2.4 Data Management and Analysis

In this study, the primary objective is to analyze the effect of two independent factors: 1. Type of trocar system (AirSeal® trocar vs. standard trocars) 2. Intra-abdominal pressure (IAP: 10 vs. 15 mmHg) on the dependent factor: CO2 absorption. This will result in four (4) study arms. CO2 absorption in each arm will be compared at 15 and 60 minutes.

Justification of sample size: An effect size of 0.46 was calculated based on average CO2 absorption rates in a study comparing CO2 absorption when using the AirSeal® trocar versus standard trocars for laparoscopic renal surgery.¹ 30 patients per arm would be needed to detect an effect size of 0.46 or greater, with 80% power and a two-tailed alpha of 0.01. In order to allow for a possible 10% drop out, 132 patients will be enrolled in the study.

CO2 absorption calculation:

CO2 elimination rate = CO²³ absorption rate in order to keep patient metabolically constant.

¹ Wolf JS Jr, Monk TG, McDougall EM, et al. The extraperitoneal approach and subcutaneous emphysema are associated with greater absorption of carbon dioxide during laparoscopic renal surgery. J Urol. 1995;154:959-963.

² Ng CS, Gill IS, Sung GT, et al. Retroperitoneoscopic surgery is not associated with increased carbon dioxide absorption. J Urol. ³ 162:1268-1272

V3 022417

^{1,2}

$$\text{Carbon dioxide elimination rate} = \frac{ETCO_2 \times Vt \times RR}{(P_B - P_{H2O}) \times Wt}$$

ETCO₂: end-tidal carbon-dioxide pressure, Vt: expired tidal volume, RR: respiratory rate, P_B: barometric pressure (760 mmHg), P_{H2O}: partial pressure of water (13 mmHg), Wt: patient's weight in kilograms

General Analyses

Continuous variables will be summarized using means, standard deviations, medians, and ranges. If normally distributed, they will be analyzed using parametric tests such as T-test and analysis of variance. To find associations between continuous variables and to control by relevant covariates we will use multiple regressions. If the normality assumption is violated we will use non-parametric tests such as Mann-Whitney or Kruskal-Wallis.

[figure not shown]
Categorical variables will be summarized with frequencies and percentages and analyzed with logistic regression or categorical response models.

95% confidence intervals will be provided for descriptive statistics, as warranted.

Subject characteristics are assumed to be comparable at the start of the study (randomization design) and so no formal statistical group comparisons will be conducted on the subject characteristics.

An overall alpha-level of 0.01 will be used as a cut-point for statistical significance and all statistical tests will be two-sided. All data will be analyzed by the Columbia University Mailman School of Public Health Biostatistics team.

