2.3 Aims & Hypotheses

2.3a Specific Aim 1

To determine if there is a difference in CO2 absorption when gynecologic laparoscopy is performed using the AirSeal® valveless trocar system versus standard insufflation trocars at intra-abdominal pressures of 10 and 15mmHg

2.3a.1a Hypothesis 1a

CO2 absorption is decreased when gynecologic laparoscopy is performed using the AirSeal® valveless trocar system versus standard insufflation trocars

2.3a.1b Hypothesis 1b

CO2 absorption is decreased when gynecologic laparoscopy is performed at an intra-abdominal pressure of 10 versus 15 mmHg

2.3b Specific Aim 2

To determine if the anesthesiologists' perception of difficulty in maintaining adequate ETCO2 during gynecologic laparoscopy as measured on a 3-point likert scale differs using the AirSeal® valveless trocar system versus standard insufflation trocars at intra-abdominal pressures of 10 and 15mmHg

2.3b.1 Hypothesis 2

Maintaining adequate ETCO2 is less challenging when using the AirSeal® valveless trocar system versus standard insufflation trocars for gynecologic laparoscopy at intra-abdominal pressures of 10 and 15 mmHg

2.3c Specific Aim 3

To determine if the surgeon's visualization of the operative field during gynecologic laparoscopy as measured on a visual analog scale (VAS) differs when using the AirSeal® valveless trocar system versus standard insufflation trocars at intra-abdominal pressures of 10 and 15 mmHg

2.3c.1 Hypothesis 3

Visualization of the operative field is improved when using the AirSeal® valveless trocar system versus standard insufflation trocars for gynecologic laparoscopy at intra-abdominal pressures of 10 and 15 mmHg

2.3d Specific Aim 4

To determine if post-operative shoulder pain as measured on a VAS pain scale differs following gynecologic laparoscopy using the AirSeal® valveless trocar system versus standard insufflation trocars at intra-abdominal pressures of 10 and 15 mmHg

2.3d.1 Hypothesis 4

Post-operative shoulder pain is improved following gynecologic laparoscopy using the AirSeal® valveless trocar system versus standard insufflation trocars at intra-abdominal pressures of 10 and 15 mmHg

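### Hypotheses 1a and 1b concern two crossed factors, but section 2.4 describes the comparison by arm and names no two-factor model or main-effect contrast to test them

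*Combined protocol and SAP*

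**What the plan says.** Section 2.4 opens with a two-factor aim: "the primary objective is to analyze the effect of two independent factors: 1. Type of trocar system", with intra-abdominal pressure (10 v 15 mmHg) as the second factor and CO2 absorption as the outcome. Section 2.3 gives each factor its own hypothesis. Hypothesis 1a reads "CO2 absorption is decreased when gynecologic laparoscopy is performed using the AirSeal® valveless trocar system versus standard insufflation trocars". Hypothesis 1b reads "CO2 absorption is decreased when gynecologic laparoscopy is performed at an intra-abdominal pressure of 10 versus 15 mmHg".

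The sentence that describes the comparison is about arms: "This will result in four (4) study arms. CO2 absorption in each arm will be compared at 15 and 60 minutes". The sample size is also per arm: "30 patients per arm would be needed to detect an effect size of 0.46 or greater, with 80% power and a two-tailed alpha of 0.01".

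The General Analyses text lists t-test and analysis of variance for normal data, multiple regression for associations and covariate control, and then a fallback: "If the normality assumption is violated we will use non-parametric tests such as Mann-Whitney or Kruskal-Wallis". The number of factors in the analysis of variance and the terms in the regression are not given. The same section sets an overall two-sided alpha of 0.01.

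**The concern.** Hypotheses 1a and 1b each ask about one factor, and the 2x2 layout lets every woman contribute to both. The methods listed can be applied in ways that differ in what they test and how well:

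- A t-test or Mann-Whitney between two arms uses 60 of the 120 evaluable women and answers a question at one level of the other factor.
- A one-way analysis of variance or Kruskal-Wallis over four arms uses everyone, but its 3-df result says only that the arms differ somewhere. It does not say whether trocar or pressure is responsible.
- A two-group test on one factor, pooled over the other, does address 1a or 1b with all women, but leaves the other factor's effect in the error.
- A two-factor model tests each hypothesis on all women with the other factor taken out of the error.

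The plan does not say which of these is primary. The rank fallback, triggered by how the data look, would also drop the two-factor structure and the covariate control mentioned a few lines before. What is at stake is precision on the primary outcome and a clear link from each hypothesis to one test.

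**Working it through.** **Inputs (section 2.4).** Effect size 0.46, metric not stated; 30 per arm; 80% power; two-sided alpha 0.01; 10% dropout; 132 enrolled. Assumed here: equal arms, common SD, normal outcome, one time point, alpha 0.01 for each test. Power is from the noncentral t or F distribution.

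**The plan's own figure.** Two groups, n per group, difference d in SD units: noncentrality = d × √(n/2).
- 0.46 read as Cohen's d: 113 per arm (111 by normal approximation). Does not reproduce 30.
- 0.46 read as Cohen's f for two groups, so d = 2 × 0.46 = 0.92: 30 per arm (28 by normal approximation). Reproduces, with 81% power.
- 0.46 read as f for a four-arm 3-df test: 20 per arm. For a main effect in the 2x2: 15 per arm.

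Of the readings tried, only a 30 v 30 comparison at d = 0.92 gives 30 per arm. Enrolment: 120 × 1.10 = 132, as stated.

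**Detectable difference at 80% power.** The normal approximation is (2.576 + 0.842) × SE = 3.417 × SE, with SE in SD units.

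| Analysis | SE | Normal | Exact |
|---|---|---|---|
| Arm pair, 30 v 30, 58 df | √(2/30) = 0.258 | 0.88 | 0.91 |
| Four-arm test, 3 and 116 df, effect in one factor only | – | – | 0.74 |
| Two-factor main effect, 60 v 60, 116 df | √(2/60) = 0.183 | 0.62 | 0.63 |
| Interaction (difference of differences), 116 df | √(4/30) = 0.365 | 1.25 | 1.27 |

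**Pooled two-group t-test ignoring the other factor.** If the other factor has effect p (in SD), the error variance becomes 1 + p²/4.
- p = 0: variance 1; detectable difference 0.63 SD.
- p = 0.3: variance 1 + 0.09/4 = 1.0225; 0.633 × √1.0225 = 0.64 SD.
- p = 0.92: variance 1 + 0.8464/4 = 1.21; 0.633 × √1.21 = 0.70 SD.

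The documents give no pressure effect, so p is an assumption and 0 to 0.92 SD is shown as a range.

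**Power for a true effect in one factor.**

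| True effect | Arm pair | Four-arm F | Two-factor main effect |
|---|---|---|---|
| 0.46 SD | 20% | 29% | 46% |
| 0.63 SD | 42% | 62% | 80% |
| 0.92 SD | 81% | 96% | 99% |

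At 0.63 SD, Kruskal-Wallis had about 59% in a simulation with normal data (4,000 runs), close to the four-arm F. The pooled t-test has 80% with p = 0, 78% with p = 0.3 and 70% with p = 0.92.

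**Sharing alpha.** If the overall 0.01 is split by Bonferroni over 1a and 1b (0.005 each), the two-factor figure rises from 0.63 to 0.68 SD. Split over two times as well (0.0025 each), it is 0.72 SD.

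**The case against.** A reader might infer that the plan is committed to arm-by-arm tests and so throws away half the women. The documents do not support that. Section 2.4 states a two-factor objective, and analysis of variance and multiple regression can both carry two factors. Only the pairwise reading uses half the women. The gap is that no model is named.

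A reader might also infer a free gain from 0.91 to 0.63 SD. But 0.91 SD is the baseline only for pairwise tests. For a four-arm test it is about 0.74 SD, and a pooled t-test is already at 0.63 to 0.70 SD. The upper end of that last range needs a pressure effect of 0.92 SD, for which the documents give no basis: the planning effect came from a trocar comparison, and section 1.0 cites a review that found similar end-tidal CO2 and pCO2 at low and standard pressure (with one pelvic study). Nor is the gain without a price, since a main effect averages over the other factor.

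Two further points stand in part. If 0.46 means d = 0.92, even an arm pair has 81% power, so no reading is underpowered for that effect. And the objectives compare trocars at 10 and 15 mmHg, which can be read as within-pressure contrasts; the rationale that the valveless system may permit lower pressure points the same way. That is a reason to report the arm means and the interaction. It does not supply a test for 1a and 1b as worded.

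The rank tests are introduced only as examples for continuous variables in general, and on normal data Kruskal-Wallis costs about 3 points of power against the four-arm F. The case against them here is the lost factor structure.

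**Conclusion.** The concern holds in this form: two single-factor hypotheses are stated, the comparison and sample size are described by arm, and no two-factor model or main-effect contrast is named as their test. Depending on the reading, the detectable difference is anywhere from 0.63 to 0.91 SD with the same 120 evaluable women, and the four-arm test would not attribute a difference to either factor. The documents do not show that the weakest reading is the intended one, although the stated 30 per arm matches a 30 v 30 comparison.

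The figures rest on 30 evaluable per arm, a common SD, normal data and 0.01 per test at one time. The main-effect figure is easy to interpret only if the interaction is small, and the trial has 80% power only for an interaction of about 1.27 SD. This should be changed because the better method costs only wording. It does not invalidate the design.

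**What to change.** In section 2.4, state the primary analysis as a linear model of the CO2 rate with trocar and pressure as two factors, testing the trocar main effect for 1a and the pressure main effect for 1b on all women. Name either 15 or 60 minutes as primary, or model both times together allowing for the repeated measurement, and say how the overall alpha of 0.01 is shared across hypotheses and times. Report the trocar-by-pressure interaction and the four arm means, all with confidence intervals.

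If residuals are skewed, keep both factors: for example, analyse the log of the rate (natural here, as the rate is a product and quotient of its inputs), use robust standard errors, or use a permutation test, in place of Mann-Whitney or Kruskal-Wallis.

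The cost is SAP wording, with no extra patients or measurements. The downside to state is that each main effect averages over the other factor, and that the interaction will be too imprecise to rule out a moderate dependence of one factor on the other.

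### The sample size gives the whole two-sided 0.01 to one comparison, while Aim 1 has two hypotheses at two times under an overall 0.01 that is never shared out

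*Combined protocol and SAP*

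**What the plan says.** All references are to the combined protocol and SAP.

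- **Objective (section 2.4).** "In this study, the primary objective is to analyze the effect of two independent factors", namely trocar type and intra-abdominal pressure. Crossing them gives four arms.
- **Hypotheses (section 2.3, Aim 1).** 1a: "CO2 absorption is decreased when gynecologic laparoscopy is performed using the AirSeal® valveless trocar system versus standard insufflation trocars". 1b: "CO2 absorption is decreased when gynecologic laparoscopy is performed at an intra-abdominal pressure of 10 versus 15 mmHg".
- **Times (section 2.4).** "CO2 absorption in each arm will be compared at 15 and 60 minutes". Neither time is named as primary.
- **Sample size (section 2.4).** 30 per arm "would be needed to detect an effect size of 0.46 or greater, with 80% power and a two-tailed alpha of 0.01". The 0.46 comes from a study of the same trocar against standard trocars in renal surgery. No means, SD or metric are given.
- **Tests (section 2.4, General Analyses).** If continuous variables are normally distributed, "they will be analyzed using parametric tests such as T-test and analysis of variance". No test is tied to the primary comparison.
- **Alpha (section 2.4, General Analyses).** "An overall alpha-level of 0.01 will be used as a cut-point for statistical significance". There is no adjustment, testing order or split.

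**The concern.** The sample-size sentence has one effect size, one power and all of the 0.01, so it describes a single test. The primary objective involves at least four: two factors at two times. The plan does not say whether each factor is tested as a main effect (two arms against two, 60 vs 60) or between single arms (30 vs 30), and the listed t-test and analysis of variance allow either.

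Two properties are at stake. If every test is judged at 0.01, the overall error rate is not 0.01. If 0.01 is truly overall and is shared, a comparison of two arms no longer has the stated 80% power. As written, a significant result for either factor at either time could be reported as the primary finding at an overall 0.01.

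**Working it through.** **Inputs.** From section 2.4: 30 per arm, four arms, effect size 0.46, 80% power, two-sided 0.01, times 15 and 60 minutes. Assumed, because the documents do not say: equal evaluable arms, normal data, and a correlation of 0.5 to 0.9 between the two times.

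**Step 1. Reproduce 30 per arm.** For two groups of n and a standardised difference d, the noncentrality is d√(n/2), and power comes from the noncentral t distribution.

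- 0.46 as Cohen's f, two groups: d = 2 × 0.46 = 0.92. With n = 30, noncentrality = 0.92 × √15 = 3.56, critical t (58 df) = 2.66, power **81.2%**. With n = 29, power is 79.5%. The smallest n for 80% is therefore 30, as stated.
- 0.46 as Cohen's d: noncentrality = 0.46 × √15 = 1.78, power **19.9%**; 113 per arm would be needed (111 by the normal approximation).
- f = 0.46 across four arms: the 3-df overall test needs 20 per arm, and a 1-df main effect needs 15.

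Of the readings tried, only f for one two-group test at the full 0.01 returns 30. Enrolment follows as 120 × 1.1 = 132.

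**Step 2. Error rate if each test uses 0.01.**

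- Four main-effect tests (two factors × two times): 1 − 0.99⁴ = 3.9% if independent. Simulation with correlated times gives **3.8% to 3.0%** for correlations 0.5 to 0.9.
- All six arm pairs at both times (twelve tests): 1 − 0.99¹² = 11.4% if independent; simulation gives **9.1% to 7.1%**. This is an upper case, because the plan nowhere schedules these twelve tests.

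**Step 3. Power if 0.01 is shared equally (Bonferroni).**

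| Contrast | Alpha per test | 0.92 SD (0.46 as f) | 0.46 SD (0.46 as d) |
|---|---|---|---|
| Arm pair, 30 vs 30 | 0.01 (not shared) | 81.2% | 19.9% |
| Arm pair, 30 vs 30 | 0.005 (2 tests) | 73.7% | 13.9% |
| Arm pair, 30 vs 30 | 0.0025 (4 tests) | 65.5% | 9.5% |
| Main effect, 60 vs 60 | 0.01 (not shared) | 99.2% | 46.3% |
| Main effect, 60 vs 60 | 0.005 (2 tests) | 98.4% | 37.1% |
| Main effect, 60 vs 60 | 0.0025 (4 tests) | 97.2% | 29.0% |

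For main effects the noncentrality is d√30 with 116 df. For an arm pair at 0.92 SD, 80% would need 34 per arm for two tests and 38 for four. Allowing for the correlation between times recovers little: 74–77% for one pair at two times, and 66–69% for two pairs at two times.

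**Step 4. Difference detectable with 80% power, 60 vs 60.** 0.63 SD at 0.01, 0.68 SD at 0.005 and 0.72 SD at 0.0025. These do not depend on what 0.46 means.

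**The case against.** **The word *overall* may mean a common threshold.** The sentence sits in General Analyses and calls 0.01 a cut-point, so it may set one level for every test. The two statements of 0.01 then agree, and the 81.2% is not reduced. This reading is open. On it the remaining error is that 0.01 is not the overall rate, which is 3–4% for the four main-effect tests. That is below a conventional 5%, but it is not the rate the plan states, and the plan does not say that 0.01 was chosen to allow for several tests.

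**The plan already points to main effects.** The objective speaks of two factors, 1a and 1b are factor contrasts, and analysis of variance is listed. This stands. A reader might infer twelve pairwise tests and power of 52.0% (0.01/12 per test, 0.92 SD), but the documents plan no such set. If arm pairs were tested only after a significant analysis of variance at 0.01 (also not stated), simulation puts the error at 1.7–2.1% with all arms equal, and at 4–5% when one arm differs.

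**The metric of 0.46 is inferred.** This stands too. A reader might take it as established that 30 per arm gives 80% power for an arm pair, or that main effects keep both the stated power and the stated error rate. Neither is in the documents. Both depend on 0.46 being f, and both fail if it is d.

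**No pressure effect was assumed.** The 0.46 comes from a trocar comparison, so it gives no planned power for Hypothesis 1b.

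**The family is undefined.** If *overall* covers the whole trial, Aims 2 to 4 share the 0.01 as well, and controlling only the CO2 tests would not be enough. The fix must therefore state its scope.

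**Conclusion.** The point holds in a limited form. The sample size spends the whole two-sided 0.01 on one comparison, and the plan neither shares its overall 0.01 nor names a primary contrast or time. Judging each test at 0.01 gives a 3–4% chance of at least one false positive for Hypotheses 1a and 1b as main effects, and at most 7–9% if all arm pairs were tested at both times without a gate. These rates assume a correlation between times of 0.5 to 0.9.

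The loss of power is conditional. It affects arm pairs, not main effects, and the 73.7% and 65.5% hold only if 0.46 is f. If 0.46 is d, the stated 80% is wrong before any multiplicity rule is applied, even for a main effect at the full 0.01, and must be restated. The documents do not settle which it is.

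This should be fixed before the data are analysed.

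**What to change.** Keep the enrolment and amend section 2.4 along these lines:

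> Primary analysis: the effects of trocar type and of pressure on CO2 absorption, estimated by two-way analysis of variance at 15 and at 60 minutes. The four main-effect tests (Hypotheses 1a and 1b at each time) form the primary family and are tested by Holm's procedure at an overall two-sided alpha of 0.01. This alpha covers the primary family only. Aims 2 to 4, contrasts between single arms and the trocar-by-pressure interaction are secondary, and are reported as estimates with confidence intervals. With 60 vs 60 evaluable women and 0.0025 per test, power is about 80% for 0.72 SD and 97% for 0.92 SD.

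Alternatively, name one time as primary and share 0.01 over two tests. The figures are then 0.68 SD for 80% power, and 98% for 0.92 SD.

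Also:

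- Label 0.46 as d or f, with the means and SD behind it. If it is d, correct the stated 80%.
- Say that 0.46 comes from a trocar comparison and that no pressure effect was assumed.
- If 0.01 was meant per test, delete the word *overall* and state the 3–4% family-wise error.

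**Cost.** A change of wording and of analysis priority, with no extra patients. Contrasts between single arms lose primary status. Each main effect averages over the other factor, so a strong interaction would have to be read from the secondary estimates. Simple randomization may leave the groups somewhat unequal, so the power figures are approximate. If 0.46 proves to be d, the change still controls the error rate but does not restore 80% power for that effect.

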1.0 STUDY PURPOSE AND RATIONALE

Conventional and robotic-assisted laparoscopic procedures have become increasingly favored by gynecologists and their patients worldwide. As these minimally invasive techniques become more widespread, the surgeon has to be aware of, and respond to, different factors that will affect a patient's cardiopulmonary status during the procedure.

Three main factors affect patients' cardiopulmonary status during gynecologic laparoscopy.

During standard gynecologic laparoscopy, a 25-30° Trendelenburg tilt is needed to visualize the pelvic anatomy. In addition, an intra-abdominal pressure (IAP) of 10 to 20 mmHg is maintained with a continuous infusion of CO2 at a flow rate of 40L/min. The Trendelenburg tilt causes cardiovascular and gas exchange impairments that are exaggerated by the CO2 pneumoperitoneum.³ These factors affect the anesthesiologists' ability to ventilate the patient and maintain adequate end-tidal CO2 (ETCO2). Furthermore, CO2 which is the most commonly used gas for laparoscopy is absorbed transperitoneally and this absorption combined with hypercapnia and hypoventilation can lead to cardiac arrhythmias and even cardiac arrest.⁴ Multiple studies have demonstrated increased systemic absorption of CO2 gas during transperitoneal and retroperitoneal laparoscopy by measuring end-tidal CO2 (ETCO2) and CO2 elimination rates.^{5,6}

In attempts to minimize the effects of CO2 pneumoperitoneum, various modifications to traditional laparoscopy have been explored including gasless and/or low-pressure pneumoperitoneum, and use of alternate gases (nitrous oxide, argon, helium) for insufflation; all with varying degrees of success.^{7,8,9,10,11}

The AirSeal® valveless trocar system has the potential to minimize patient complications by decreasing systemic absorption of CO2 gas.

The AirSeal® valveless trocar system was designed to provide "stable pneumoperitoneum at a CO2 flow rate of 3L/min, continuous smoke evacuation and valve free access to the abdominal cavity"¹². Use of this system is also associated with a decrease in CO2 use, absorption and elimination when compared to standard trocars.¹ This reduction in CO2 absorption potentially makes the AirSeal® trocar system a more attractive alternative to standard insufflation. However to date, no randomized clinical trials have been performed to demonstrate clinically or statistically significant benefits of the AirSeal® trocar system until now.

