2.5 Graphical schema of study

3.0 STUDY PROCEDURES

- . / In the pre-operative area, subjects will be randomized via sealed, opaque envelopes containing a simple randomization scheme to one of the four groups:
 - Group A: Standard trocar/IAP 15 mmHg
 - Group B: Standard trocar/IAP 10 mmHg
 - Group C: AirSeal® trocar /IAP 15 mmHg
 - Group D: AirSeal® trocar /IAP 10 mmHg
- . / All intraoperative staff assigned to the patient will be made aware of her participation in the study. The delegated research staff will fill out all pre-operative data. (CRF1)
- . / Once in the operating room, standard surgical positioning, prepping and draping will be performed.
- . / The patient's randomization group will be stated at the surgical TIME OUT.
- . / Proposed surgery will commence using the AirSeal® or standard trocar at IAP of either 10 or 15 mmHg.
- . / All cases will be performed with routine general endotracheal anesthesia. Ventilatory parameters and settings will be at the discretion of the anesthesiologists.
- . / Pneumoperitoneum will be established using the Veress needle and trocar insertion performed at 20 mmHg.
- . / Immediately following trocar insertion/port placement, pressure will be decreased to 10 or 15 mmHg.
- . / If at any point the surgeon or anesthesiologist feels that the patient's safety is in question, necessary changes, including increasing the intra-abdominal pressure or switching between trocars, will be made expeditiously, and recorded.
- . / During surgery, "surgical data" and "anesthesia data" variables will be filled. (CRF 3 & 4)
- . / Following surgery 'General intraoperative data' variables listed below will be collected. (CRF 2)
- . / At the end of the case, the surgeon and the anesthesiologist will complete questionnaires (CRF 3 & 4)
- . / Post-operatively, the patient will fill out Visual Analog Scale pain scores at specified time periods. (CRF 5)
- . / PACU/nursing staff will fill out a questionnaire indicating pain medication used during recovery and post-operative recovery time (CRF 6)

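### The primary outcome is called CO2 absorption but measures total exhaled CO2, and the available analysis text names no pre-insufflation covariate: relabel it and adjust; the between-arm test itself stands

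*Combined protocol and SAP*

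**What the plan says.** Section 2.4 (Data Management and Analysis) makes CO2 absorption the dependent variable and obtains it by equating the elimination rate with the "absorption rate in order to keep patient metabolically constant". The elimination rate is ETCO2 × Vt × RR / ((P_B − P_H2O) × Wt), with P_B = 760 mmHg and P_H2O = 13 mmHg. On timing, "CO2 absorption in each arm will be compared at 15 and 60 minutes". On covariates, the section says only that "to control by relevant covariates we will use multiple regressions"; none is named.

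Section 1.0 says that earlier studies showed absorption "by measuring end-tidal CO2 (ETCO2) and CO2 elimination rates", so the surrogate is disclosed and has precedent. The same section lists absorption and elimination as separate quantities.

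Section 3.0 bears on when a baseline could be read. Its steps include:

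- "In the pre-operative area, subjects will be randomized via sealed, opaque envelopes"
- "All intraoperative staff assigned to the patient will be made aware of her participation in the study"
- the patient's "randomization group will be stated at the surgical TIME OUT"
- "Ventilatory parameters and settings will be at the discretion of the anesthesiologists"

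The case report forms, a figure in section 2.4 and the schema in section 2.5 are not in the available text.

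**The concern.** The formula has no term that removes metabolic CO2. The phrase about keeping the patient metabolically constant can be read as assuming constant metabolic production. That assumption would let a difference in elimination be read as a difference in absorption. It would not make the level of elimination equal to absorption, because the formula is clearly positive before any gas is insufflated.

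Two things are at stake. First, absorption is the primary objective (section 2.2.1) and the subject of Hypotheses 1a and 1b. Arm-level rates and percentage reductions published under that name would mislead about the size of the effect. Second, patients differ in metabolic CO2 output even per kilogram, and that variation stays in the error term. A pre-insufflation value of the same formula is the natural covariate to remove it.

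**Working it through.** **1. The plan's own figure.** Section 2.4 gives effect size 0.46, two-sided alpha 0.01, 80% power and 30 per arm. It does not say whether 0.46 is Cohen's d or f. With a two-sample t test:

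- If 0.46 is f for two groups, d = 2 × 0.46 = 0.92, which needs 30 per arm (power 81.2%). This reproduces the plan.
- If 0.46 is d, 113 per arm are needed. At 30 v 30 power is 19.9%, and at 60 v 60 it is 46.3%.
- Enrolment: 120 × 1.1 = 132, as stated.

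The two main effects compare 60 v 60; single-arm pairs compare 30 v 30.

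**2. What the formula returns without absorption.** Assumed pre-insufflation inputs: ETCO2 35 mmHg, Vt 500 mL, RR 12, weight 70 kg.

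- Central: 35 × 500 × 12 / (747 × 70) = 4.02 mL/kg/min
- Low (ETCO2 30, Vt 400, RR 10): 30 × 400 × 10 / (747 × 70) = 2.29
- High (ETCO2 40, Vt 500, RR 14): 40 × 500 × 14 / (747 × 70) = 5.35

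The formula also applies end-tidal CO2 to the whole tidal volume, so it only approximates elimination. With an assumed dead-space share of 20 or 40%, 4.02 becomes 3.21 or 2.41.

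**3. Effect on percentage reductions.** If metabolic CO2 is a share s of measured elimination, a 30% cut in absorption appears as 30% × (1 − s). For assumed s = 30, 50 and 80%, that is 21, 15 and 6%.

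**4. Validity of the test.** Write elimination as metabolic plus absorbed CO2, with metabolic production independent of arm. In 40,000 simulated trials the unadjusted t test had type I error 0.0100 (30 v 30) and 0.0104 (60 v 60) at nominal 0.01. A true absorption difference of −0.50 came back as −0.50.

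**5. Precision forgone.** Let r be the correlation between the pre-insufflation and intra-operative rates. The documents do not give it, so a range is assumed. ANCOVA multiplies the residual SD by √(1 − r²) and costs one degree of freedom, so power is computed at d/√(1 − r²). Half-widths are for 99% intervals, t × √(2/n) × √(1 − r²), in SD units.

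| | unadjusted | r = 0.1 | r = 0.3 | r = 0.5 | r = 0.7 |
|---|---|---|---|---|---|
| Interval narrowing | – | 0.5% | 5% | 13% | 29% |
| Half-width, 30 v 30 | 0.69 | 0.69 | 0.66 | 0.60 | 0.49 |
| Half-width, 60 v 60 | 0.48 | 0.48 | 0.46 | 0.41 | 0.34 |
| Power if f = 0.46, 30 v 30 | 81% | 82% | 85% | 92% | 99% |
| Power if f = 0.46, 60 v 60 | 99.2% | 99.2% | 99.6% | 99.9% | >99.9% |
| Power if d = 0.46, 30 v 30 | 20% | 20% | 22% | 28% | 44% |
| Power if d = 0.46, 60 v 60 | 46% | 47% | 51% | 61% | 82% |

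**6. Why the timing of the reading matters.** If the anaesthesia team knows the arm and its ventilation shifts the covariate by δ SD, ANCOVA is biased by r × δ (equal SDs assumed). For an assumed δ = 0.2 and r = 0.3, 0.5 and 0.7, the bias is 0.06, 0.10 and 0.14 SD. The 60 v 60 false-positive rate rises from 1% to 1.4, 2.6 and 6.5%.

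**7. Missing baselines.** If a share m is filled with the overall mean, the residual variance is 1 − r²(1 − m). For m = 20% and r = 0.3, 0.5 and 0.7, that is 0.928, 0.800 and 0.608. Power at 30 v 30 (d = 0.92) is then 84.5, 90.2 and 96.8%, still above 81%.

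**The case against.** The strongest reply is that nothing in the primary test is broken. The formula is printed, the surrogate is declared and has precedent, and randomisation balances metabolic CO2 in expectation. All of that stands. A reader might infer that including metabolic CO2 biases the arm comparison or invalidates the primary analysis. The documents do not support that: the test of elimination keeps its size.

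It can also be said that Hypotheses 1a and 1b are main effects, and that on the reading of 0.46 that reproduces 30 per arm they already have 99% power. That stands for power. It does not follow that precision matters only for 30 v 30 pairs. Interval narrowing is proportionally the same at both sizes, and if 0.46 is d the 60 v 60 power gain is the larger one at r from 0.3 to 0.7.

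The gain also depends on an assumed r. Ventilation is discretionary, so r could be low: at r = 0.1 or 0.2, 30 v 30 power moves from 81.2% only to 81.6 or 83.0%. Finally, the forms that record anaesthesia data are not visible, and the sentence on relevant covariates would permit this one. So the documents do not show that no baseline is taken, only that the available analysis text does not name it. Collecting a value is still not the same as prespecifying its use.

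**Conclusion.** The label is wrong for arm-level rates and percentage reductions, and this does not depend on the exact inputs: the formula is positive when absorption is zero. About 4.0 mL/kg/min (2.3 to 5.4) is its size under the assumed inputs. The between-arm test of elimination is valid. Reading its difference as a difference in absorption further assumes that metabolic production, CO2 stores and ventilation do not differ by arm. Section 3.0 leaves ventilation to clinicians who hear the group at TIME OUT.

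Not naming a pre-insufflation covariate forgoes precision, from almost nothing at r = 0.1 to intervals 29% narrower at r = 0.7. A reader might infer that the trial therefore falls short of its stated 80% power. The documents do not show this, because the SD behind the effect size may already include metabolic variation. The ambiguity between d and f is a separate matter that adjustment does not settle. Overall this is a minor point with a cheap remedy.

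**What to change.** 1. Call the outcome CO2 elimination rate (end-tidal estimate) in the objectives, hypotheses, analysis and reports. Report elimination minus the pre-insufflation value only as a descriptive estimate of absorption. State that it assumes stable metabolic production, CO2 stores and gas exchange; section 1.0 itself says that tilt and pneumoperitoneum impair gas exchange.
2. Prespecify an ANCOVA of the elimination rate at 15 and at 60 minutes on trocar type and pressure, with the pre-insufflation elimination rate as covariate. Take ETCO2, Vt and RR from the anaesthesia record after intubation, before insufflation and before the anaesthesia team knows the group, and record the time. Treat later readings as missing and fill them with the overall mean, ignoring arm, so that no patient is lost. Give the unadjusted comparison as a sensitivity analysis.

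The cost is one time-stamped ventilator reading per patient if it is not already collected, one degree of freedom and a change of wording. It also needs a concealment step: the group must be withheld from the anaesthesia team until the reading is recorded. Section 3.0 randomises in the pre-operative area and does not say whether the team learns the group before TIME OUT. If r is low the gain is negligible, but almost nothing is lost: at r = 0, 60 v 60 power for d = 0.46 is 46.3% either way. A baseline covariate does not correct for ventilation that differs by arm later in surgery.
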